#### 6.1.1 Tumor data

- The tumor disease information that will be documented and verified at the screening visit for each subject includes the following. All these details will be documented in patient's history and physical exam and also recorded in the C3D database.
- Detailed history of the tumor, including histopathological diagnosis, grading and staging in accordance with the Union Internationale Contre le Cancer Tumor Node Metastasis Classification at diagnosis (UICC TNM).
  - The T and M category (T1-3 vs T4 and M0 or M1) of the tumor at the time of study entry, based on screening assessments
- All therapy used for prior treatment of the tumor (including surgery, radiotherapy and chemotherapy, immunotherapy).
- Any other conditions that were treated with chemotherapy, radiation therapy, or immunotherapy.

#### 6.1.2 Concomitant Medications and Therapies

All concomitant medications taken by the subject during the trial, from the date of signature of informed consent are to be recorded in the appropriate section of the eCRF, noting the name, dose, duration and indication of each drug. Nondrug interventions (other than vitamins) and any changes to a concomitant medication or other intervention should also be recorded in the eCRF.

#### 6.1.3 DATA ELEMENTS

- Documentation of dosage and timing of drug administration
- Outside laboratory, radiologic, and pathology results will be sent to the PI and entered into NCI C3D at NIH

- NIH labs and tests will be downloaded into C3D

## **6.2 DATA SHARING PLANS**

### **6.2.1 Human Data Sharing Plan**

Human data generated in this research for future research will be shared as follows:

- Coded, linked data in an NIH-funded or approved public repository.
- Coded, linked data in another public repository.
- Identified or coded, linked data in BTRIS (automatic for activities in the Clinical Center)

Data will be shared through:

- An NIH-funded or approved public repository: clinicaltrials.gov, dbGaP
- BTRIS (automatic for activities in the Clinical Center)
- Approved outside collaborators under appropriate individual agreements.
- Publication and/or public presentations.

Data will be shared:

- Before publication.
- At the time of publication or shortly thereafter.

### **6.2.2 Genomic Data Sharing Plan**

Unlinked genomic data will be deposited in public genomic databases such as dbGaP in compliance with the NIH Genomic Data Sharing Policy.

## **6.3 RESPONSE CRITERIA**

For the purposes of this study, patients should be re-evaluated for response every 8 weeks. After one year response evaluation will be done every 12 weeks. In addition to a baseline scan, confirmatory scans should also be obtained 4-8 weeks (not less than 4 weeks) following initial documentation of objective response.

Response and progression will be evaluated in this study using the new international criteria proposed by the revised Response Evaluation Criteria in Solid Tumors (RECIST) guideline (version 1.1) [45]. Changes in the largest diameter (unidimensional measurement) of the tumor lesions and the shortest diameter in the case of malignant lymph nodes are used in the RECIST criteria.

### **6.3.1 Disease Parameters**

Measurable disease: Measurable lesions are defined as those that can be accurately measured in at least one dimension (longest diameter to be recorded) as:

- By CT scan:
  - Scan slice thickness 5 mm or under: as  $\geq 10$  mm
  - Scan slice thickness  $>5$  mm: double the slice thickness

- With calipers on clinical exam:  $\geq 10$  mm.

All tumor measurements must be recorded in millimeters (or decimal fractions of centimeters).

Malignant lymph nodes. To be considered pathologically enlarged and measurable, a lymph node must be  $\geq 15$  mm in short axis when assessed by CT scan (CT scan slice thickness recommended to be no greater than 5 mm). At baseline and in follow-up, only the short axis will be measured and followed.

Non-measurable disease. All other lesions (or sites of disease), including small lesions (longest diameter  $< 10$  mm or pathological lymph nodes with  $\geq 10$  to  $< 15$  mm short axis), are considered non-measurable disease. Bone lesions, leptomeningeal disease, ascites, pleural/pericardial effusions, lymphangitis cutis/pulmonitis, inflammatory breast disease, and abdominal masses (not followed by CT or MRI), are considered as non-measurable.

Note: Cystic lesions that meet the criteria for radiographically defined simple cysts should not be considered as malignant lesions (neither measurable nor non-measurable) since they are, by definition, simple cysts.

‘Cystic lesions’ thought to represent cystic metastases can be considered as measurable lesions, if they meet the definition of measurability described above. However, if non-cystic lesions are present in the same patient, these are preferred for selection as target lesions.

Target lesions. All measurable lesions up to a maximum of 2 lesions per organ and 5 lesions in total, representative of all involved organs, should be identified as **target lesions** and recorded and measured at baseline. Target lesions should be selected on the basis of their size (lesions with the longest diameter), be representative of all involved organs, but in addition should be those that lend themselves to reproducible repeated measurements. It may be the case that, on occasion, the largest lesion does not lend itself to reproducible measurement in which circumstance the next largest lesion which can be measured reproducibly should be selected. A sum of the diameters (longest for non-nodal lesions, short axis for nodal lesions) for all target lesions will be calculated and reported as the baseline sum diameters. If lymph nodes are to be included in the sum, then only the short axis is added into the sum. The baseline sum diameters will be used as reference to further characterize any objective tumor regression in the measurable dimension of the disease.

Non-target lesions. All other lesions (or sites of disease) including any measurable lesions over and above the 5 target lesions should be identified as non-target lesions and should also be recorded at baseline. Measurements of these lesions are not required, but the presence, absence, or in rare cases unequivocal progression of each should be noted throughout follow-up.

### 6.3.2 Methods for Evaluation of Measurable Disease

All measurements should be taken and recorded in metric notation using a ruler or calipers. All baseline evaluations should be performed as closely as possible to the beginning of treatment and never more than 4 weeks before the beginning of the treatment.

The same method of assessment and the same technique should be used to characterize each identified and reported lesion at baseline and during follow-up. Imaging-based evaluation is preferred to evaluation by clinical examination unless the lesion(s) being followed cannot be imaged but are assessable by clinical exam.

Conventional CT and MRI: This guideline has defined measurability of lesions on CT scan based on the assumption that CT slice thickness is 5 mm or less. If CT scans have slice thickness greater than 5 mm, the minimum size for a measurable lesion should be twice the slice thickness. MRI is also acceptable in certain situations (e.g. for body scans).

Use of MRI remains a complex issue. MRI has excellent contrast, spatial, and temporal resolution; however, there are many image acquisition variables involved in MRI, which greatly impact image quality, lesion conspicuity, and measurement. Furthermore, the availability of MRI is variable globally. As with CT, if an MRI is performed, the technical specifications of the scanning sequences used should be optimized for the evaluation of the type and site of disease. Furthermore, as with CT, the modality used at follow-up should be the same as was used at baseline and the lesions should be measured/assessed on the same pulse sequence. It is beyond the scope of the RECIST guidelines to prescribe specific MRI pulse sequence parameters for all scanners, body parts, and diseases. Ideally, the same type of scanner should be used and the image acquisition protocol should be followed as closely as possible to prior scans. Body scans should be performed with breath-hold scanning techniques, if possible.

### 6.3.3 Response Criteria

#### 6.3.3.1 Evaluation of Target Lesions

Complete Response (CR): Disappearance of all target lesions. Any pathological lymph nodes (whether target or non-target) must have reduction in short axis to <10 mm.

Partial Response (PR): At least a 30% decrease in the sum of the diameters of target lesions, taking as reference the baseline sum of diameters.

Progressive Disease (PD): At least a 20% increase in the sum of the diameters of target lesions, taking as reference the smallest sum on study (this includes the baseline sum if that is the smallest on study). In addition to the relative increase of 20%, the sum must also demonstrate an absolute increase of at least 5 mm. (Note: the appearance of one or more new lesions is also considered progressions).

Stable Disease (SD): Neither sufficient shrinkage to qualify for PR nor sufficient increase to qualify for PD, taking as reference the smallest sum of diameters while on study.

#### 6.3.3.2 Evaluation of Non-Target Lesions

Complete Response (CR): Disappearance of all non-target lesions and normalization of tumor marker level. All lymph nodes must be non-pathological in size (<10 mm short axis).

Note: If tumor markers are initially above the upper normal limit, they must normalize for a patient to be considered in complete clinical response.

Non-CR/Non-PD: Persistence of one or more non-target lesion(s) and/or maintenance of tumor marker level above the normal limits.

Progressive Disease (PD): Appearance of one or more new lesions and/or *unequivocal progression* of existing non-target lesions. *Unequivocal progression* should not normally trump target lesion status. It must be representative of overall disease status change, not a single lesion increase.

*Abbreviated Title: Phase II M7824 in UC*  
*Version Date: 06/23/2021*

Although a clear progression of “non-target” lesions only is exceptional, the opinion of the treating physician should prevail in such circumstances, and the progression status should be confirmed at a later time by the review panel (or Principal Investigator).

#### 6.3.3.3 Evaluation of Best Overall Response

The best overall response is the best response recorded from the start of the treatment until disease progression/recurrence (taking as reference for progressive disease the smallest measurements recorded since the treatment started). The patient's best response assignment will depend on the achievement of both measurement and confirmation criteria.

**For Patients with Measurable Disease (i.e., Target Disease)**

Target Lesions	Non-Target Lesions	New Lesions	Overall Response	Best Overall Response when Confirmation is Required*
CR	CR	No	CR	≥4 wks. Confirmation**
CR	Non-CR/Non-PD	No	PR	≥4 wks. Confirmation**
CR	Not evaluated	No	PR	
PR	Non-CR/Non-PD/not evaluated	No	PR	
SD	Non-CR/Non-PD/not evaluated	No	SD	Documented at least once ≥4 wks. from baseline**
PD	Any	Yes or No	PD	no prior SD, PR or CR
Any	PD***	Yes or No	PD	
Any	Any	Yes	PD	

* See RECIST 1.1 manuscript for further details on what is evidence of a new lesion.
 
** Only for non-randomized trials with response as primary endpoint.
 
*** In exceptional circumstances, unequivocal progression in non-target lesions may be accepted as disease progression.
 
Note: Patients with a global deterioration of health status requiring discontinuation of treatment without objective evidence of disease progression at that time should be reported as “symptomatic deterioration.” Every effort should be made to document the objective progression even after discontinuation of treatment.
				

**For Patients with Non-Measurable Disease (i.e., Non-Target Disease)**

Non-Target Lesions	New Lesions	Overall Response
CR	No	CR
Non-CR/non-PD	No	Non-CR/non-PD*
Not all evaluated	No	not evaluated
Unequivocal PD	Yes or No	PD
Any	Yes	PD
* 'Non-CR/non-PD' is preferred over 'stable disease' for non-target disease since SD is increasingly used as an endpoint for assessment of efficacy in some trials so to assign this category when no lesions can be measured is not advised		

**6.3.4 Duration of Response**

Duration of overall response: The duration of overall response is measured from the time measurement criteria are met for CR or PR (whichever is first recorded) until the first date that recurrent or progressive disease is objectively documented (taking as reference for progressive disease the smallest measurements recorded since the treatment started).

The duration of overall CR is measured from the time measurement criteria are first met for CR until the first date that progressive disease is objectively documented.

Duration of stable disease: Stable disease is measured from the start of the treatment until the criteria for progression are met, taking as reference the smallest measurements recorded since the treatment started, including the baseline measurements.

**6.3.5 Progression-Free Survival**

PFS will be defined as the duration of time from start of treatment to time of progression or death, whichever occurs first.

**6.3.6 Response Review****6.3.6.1 Best overall response (BOR)**

The duration of best overall response is measured from the time measurement criteria are met for CR, PR or SD (whichever is first recorded) until the first date that recurrent or progressive disease is objectively documented (taking as reference for progressive disease the smallest measurements recorded since the treatment started).

The duration of overall CR is measured from the time measurement criteria are first met for CR until the first date that progressive disease is objectively documented.

### 6.3.6.2 Duration of stable disease

Stable disease is measured from the start of the treatment until the criteria for progression are met, taking as reference the smallest measurements recorded since the treatment started, including the baseline measurements. Stable Disease (SD) when sum of all target lesions does not qualify for CR/PR/PD for Target Lesion Response and Persistence of non-target lesions on Non-Target Lesion Response.

## 6.4 TOXICITY CRITERIA

The following adverse event management guidelines are intended to ensure the safety of each patient while on the study. The descriptions and grading scales found in the revised NCI Common Terminology Criteria for Adverse Events (CTCAE) version 5.0 will be utilized for AE reporting. All appropriate treatment areas should have access to a copy of the CTCAE version 5.0. A copy of the CTCAE version 5.0 can be downloaded from the CTEP web site ([http://ctep.cancer.gov/protocolDevelopment/electronic\\_applications/ctc.htm](http://ctep.cancer.gov/protocolDevelopment/electronic_applications/ctc.htm)).

## 7 NIH REPORTING REQUIREMENTS/DATA AND SAFETY MONITORING PLAN

### 7.1 DEFINITIONS

Please refer to definitions provided in Policy 801: Reporting Research Events found [here](#).

### 7.2 OHSRP OFFICE OF COMPLIANCE AND TRAINING / IRB REPORTING

#### 7.2.1 Expedited Reporting

Please refer to the reporting requirements in Policy 801: Reporting Research Events and Policy 802 Non-Compliance Human Subjects Research found [here](#). Note: Only IND Safety Reports that meet the definition of an unanticipated problem will need to be reported per these policies.

#### 7.2.2 IRB Requirements for PI Reporting at Continuing Review

Please refer to the reporting requirements in Policy 801: Reporting Research Events found [here](#).

### 7.3 NCI CLINICAL DIRECTOR REPORTING

Problems expeditiously reported to the OHSRP in iRIS will also be reported to the NCI Clinical Director. A separate submission is not necessary as reports in iRIS will be available to the Clinical Director.

In addition to those reports, all deaths that occur within 30 days after receiving a research intervention should be reported via email to the Clinical Director unless they are due to progressive disease.

To report these deaths, please send an email describing the circumstances of the death to [name] at [[contact]](mailto:[contact]) within one business day of learning of the death.

## **7.4 NIH REQUIRED DATA AND SAFETY MONITORING PLAN**

### **7.4.1 Principal Investigator/Research Team**

The clinical research team will meet on a weekly basis when patients are being actively treated on the trial to discuss each patient. Decisions about dose level enrollment and dose escalation if applicable will be made based on the toxicity data from prior patients.

All data will be collected in a timely manner and reviewed by the principal investigator or a lead associate investigator. Events meeting requirements for expedited reporting as described in Section **7.2.1** will be submitted within the appropriate timelines.

The principal investigator will review adverse event and response data on each patient to ensure safety and data accuracy. The principal investigator will personally conduct or supervise the investigation and provide appropriate delegation of responsibilities to other members of the research staff.

## **8 SPONSOR PROTOCOL/SAFETY REPORTING**

### **8.1 DEFINITIONS**

#### **8.1.1 Adverse Event**

Any untoward medical occurrence in a patient or clinical investigation subject administered a pharmaceutical product and which does not necessarily have a causal relationship with this treatment. An adverse event (AE) can therefore be any unfavorable and unintended sign (including a clinically significant abnormal laboratory finding), symptom, or disease temporally associated with the use of a medicinal (investigational) product, whether or not related to the medicinal (investigational) product [(ICH E6 (R2))].

#### **8.1.2 Serious Adverse Events (SAE)**

An adverse event or suspected adverse reaction is considered serious if in the view of the investigator or the sponsor, it results in any of the following:

- Death,
- A life-threatening adverse event (see Section **8.1.3**)
- Inpatient hospitalization or prolongation of existing hospitalization
  - A hospitalization/admission that is pre-planned (i.e., elective or scheduled surgery arranged prior to the start of the study), a planned hospitalization for pre-existing condition, or a procedure required by the protocol, without a serious deterioration in health, is not considered a serious adverse event.
  - A hospitalization/admission that is solely driven by non-medical reasons (e.g., hospitalization for patient convenience) is not considered a serious adverse event.
  - Emergency room visits or stays in observation units that do not result in admission to the hospital would not be considered a serious adverse event. The reason for seeking medical care should be evaluated for meeting one of the other serious criteria.

- Persistent or significant incapacity or substantial disruption of the ability to conduct normal life functions
- A congenital anomaly/birth defect.
- Important medical events that may not result in death, be life-threatening, or require hospitalization may be considered a serious adverse drug experience when, based upon appropriate medical judgment, they may jeopardize the patient or subject and may require medical or surgical intervention to prevent one of the outcomes listed in this definition.

### 8.1.3 Life-threatening

An adverse event or suspected adverse reaction is considered "life-threatening" if, in the view of either the investigator or sponsor, its occurrence places the patient or subject at immediate risk of death. It does not include an adverse event or suspected adverse reaction that, had it occurred in a more severe form, might have caused death. (21CFR312.32).

### 8.1.4 Severity

The severity of each Adverse Event will be assessed utilizing the CTCAE version 5.

### 8.1.5 Relationship to Study Product

All AEs will have their relationship to study product assessed using the terms: related or not related.

- Related – There is a reasonable possibility that the study product caused the adverse event. Reasonable possibility means that there is evidence to suggest a causal relationship between the study product and the adverse event.
- Not Related – There is not a reasonable possibility that the administration of the study product caused the event.

### 8.1.6 Adverse Events of Special Interest (AESI)

Adverse events of special interest (AESIs) are serious or nonserious AEs that are of clinical interest and should be closely followed.

AESIs include following:

- Infusion-related reactions including immediate hypersensitivity.
- Immune-related adverse events.
- M7824 mediated skin reactions.
- Anemia.
- Bleeding AEs

## 8.2 ASSESSMENT OF SAFETY EVENTS

AE information collected will include event description, date of onset, assessment of severity and relationship to study product and alternate etiology (if not related to study product), date of resolution of the event, seriousness and outcome. The assessment of severity and relationship to the study product will be done only by those with the training and authority to make a diagnosis and listed on the Form FDA 1572 as the site principal investigator or sub-investigator. AEs

occurring during the collection and reporting period will be documented appropriately regardless of relationship. AEs will be followed through resolution.

SAEs will be:

- Assessed for severity and relationship to study product and alternate etiology (if not related to study product) by a licensed study physician listed on the Form FDA 1572 as the site principal investigator or sub-investigator.
- Recorded on the appropriate SAE report form, the medical record and captured in the clinical database.
- Followed through resolution by a licensed study physician listed on the Form FDA 1572 as the site principal investigator or sub-investigator.

For timeframe of recording adverse events, please refer to Section **6.1**. All serious adverse events recorded from the time of first investigational product administration must be reported to the sponsor with the exception of any listed in Section **8.4**.

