#### **5.1.8 Multiplex Immunohistochemistry**

To correlate baseline expression of PD-L1 (on tumor cells, tumor-infiltrating immune cells or both) with activity of study drug. To evaluate modulation of intratumoral immune contexture / immunophenotype (i.e. CD3, CD8, CD4, FoxP3) in response to study drug compared with baseline.

- In the case of existing (pre-treatment) FFPE slide/blocks already available for the consenting patients, the sample will be transferred to the Laboratory of Pathology (LP).
- For patients undergoing dedicated research biopsies (baseline or on-treatment C3D1), tissue will be sent to the Laboratory of Pathology (LP) for accessioning, processing overnight in formalin and embedding in paraffin (FFPE).

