## **6 DATA COLLECTION AND EVALUATION**

### **6.1 DATA COLLECTION**

The PI will be responsible for overseeing entry of data into an in-house password protected electronic system (C3D) and ensuring data accuracy, consistency and timeliness. The principal investigator, associate investigators/research nurses and/or a contracted data manager will assist with the data management efforts. Primary and final analyzed data will have identifiers so that research data can be attributed to an individual human subject participant.

All adverse events, including clinically significant abnormal findings on laboratory evaluations, regardless of severity, will be followed until return to baseline or stabilization of event.

Document AEs from the first study drug administration, Study Day 1, through 30 days after the end of treatment. Beyond 30 days after the last dose of study drug, only adverse events which are serious and related to the study intervention need to be recorded.

An abnormal laboratory value will be recorded in the database as an AE **only** if the laboratory abnormality is characterized by any of the following:

- Results in discontinuation from the study
- Is associated with clinical signs or symptoms
- Requires treatment or any other therapeutic intervention
- Is associated with death or another serious adverse event, including hospitalization.
- Is judged by the investigator to be of significant clinical impact
- If any abnormal laboratory result is considered clinically significant, the investigator will provide details about the action taken with respect to the test drug and about the patient's outcome.

**End of study procedures:** Data will be stored according to HHS, FDA regulations, and NIH Intramural Records Retention Schedule as applicable.

**Loss or destruction of data:** Should we become aware that a major breach in our plan to protect subject confidentiality and trial data has occurred, this will be reported expeditiously per requirements in Section [7.2.1](#).

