### **8.3 REPORTING OF SERIOUS ADVERSE EVENTS**

Any AE that meets protocol-defined serious criteria or meets the definition of Adverse Event of Special Interest that require expedited reporting must be submitted immediately (within 24 hours of awareness) to OSRO Safety using the CCR SAE report form. Any exceptions to the expedited reporting requirements are found in Section **8.4**.

All SAE reporting must include the elements described in Section **8.1.6**.

SAE reports will be submitted to the Center for Cancer Research (CCR) at: [[contact]](mailto:[contact]) and to the CCR PI and study coordinator. CCR SAE report form and instructions can be found at:

<https://ccrod.cancer.gov/confluence/display/CCRCRO/Forms+and+Instructions>.

Following the assessment of the SAE by OSRO, other supporting documentation of the event may be requested by the OSRO Safety and should be provided as soon as possible.

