#### **12.5.1.3 Tumor Biopsy**

Needle biopsy is minimally invasive and is typically a very safe procedure. Depending upon the site being biopsied and the type of biopsy being performed, risks can include infection of the

biopsy site, development of a hematoma, and bleeding. Rarely more significant complications can occur when structures near the biopsy target are entered with the needle (e.g. puncture of lung or bowel). Surgical procedures for biopsy specimens will not be conducted for the sole purpose of research specimen collection, although when surgical biopsies are performed for clinical or NCI protocol requirements, samples may be requested as part of participation on this trial. In this instance, no added risk is incurred.

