#### 12.5.1.6 Risks of exposure to ionizing radiation

This research study involves up to 7 CT C/A/P scans and up to 3 CT-guided biopsies. Pre-treatment tissue biopsy and tissue availability is mandatory. On-treatment biopsy is required unless obtaining biopsy is not technically or clinically feasible. Post-treatment biopsy is optional. Subjects will be exposed to up to approximately 10.1 rem.

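### AE recording and sponsor SAE reporting start at the first dose, so a non-fatal serious complication of a pre-dose research biopsy, when one is done, falls outside this protocol's safety record

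*Combined protocol and SAP*

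**What the plan says.** **Safety window.** Section 6.1 sets the recording period: "Document AEs from the first study drug administration, Study Day 1, through 30 days after the end of treatment". Section 8.2 refers to 6.1 for timing and adds: "All serious adverse events recorded from the time of first investigational product administration must be reported to the sponsor". Section 8.1.1 defines an adverse event as an occurrence in a "patient or clinical investigation subject administered a pharmaceutical product". Section 8.1.5 allows two causality answers, related or not, and both concern the study product.

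**Baseline biopsy.** Section 5.1.8 has handling instructions that begin "For patients undergoing dedicated research biopsies (baseline or on-treatment C3D1". The schedule in 5.2 marks, at baseline, three snap-frozen cores for single-cell RNA-Seq and one fresh-frozen core for TCR sequencing. Section 12.5.1.6 states: "This research study involves up to 7 CT C/A/P scans and up to 3 CT-guided biopsies". It goes on to name pre-treatment, on-treatment and post-treatment biopsies. Section 12.5.1.3 lists infection, hematoma and bleeding as risks, and adds: "Rarely more significant complications can occur when structures near the biopsy target are entered with the needle (e.g. puncture of lung or bowel".

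**SAE report content.** Section 8.3 states: "All SAE reporting must include the elements described in Section 8.1.6".

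**The concern.** The protocol plans a research procedure that can take place before the first dose and describes the serious harm it can cause. It then opens its safety record only at the first dose. A patient whose lung is punctured during a fresh baseline biopsy, and who recovers, would have an event that nothing in this protocol asks anyone to enter in its AE/SAE dataset or send to its sponsor.

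What is at stake is the sponsor's view of harm from a research procedure, and a clean baseline for events that overlap dosing. Bleeding is an event of special interest under 8.1.6, so a biopsy bleed that starts before the first dose and continues after it would have no required record of its onset. Section 6.1.2 already collects concomitant medications from consent. The treatment given for a complication could therefore be on file while the complication is not.

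**Working it through.** No sample size, power or error rate enters this point. The check sets the relevant sections side by side.

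1. **Start of recording.** Sections 6.1 and 8.2 agree on the first dose. No sentence in the protocol extends AE or SAE recording to complications of study procedures before that.

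2. **Definition and causality.** Before dosing, the 8.1.1 definition is not met as worded, and 8.1.5 has no category for a study procedure.

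3. **Whose procedure is it?** Sections 5.1.8, 5.2 and 12.5.1.6 treat the baseline biopsy as this study's own. On the other side, 2.2.2 places screening under 01-C-0129, an eligibility screening and tissue procurement protocol, and lists the pre-treatment tissue item there. Appendix A puts the biopsy in its screening column. The safety rules of 01-C-0129 are not in the documents.

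4. **Is a fresh biopsy required?** The wording differs by section:
 - 2.1.1.8 and 2.2.2: biopsy and/or archival tissue.
 - 5.1.7.2 and Appendix A note 1: biopsy and/or tissue availability.
 - 5.1.7.1 (fresh/frozen tissue): conditional on a pre-treatment biopsy being done.
 - 5.2: fresh cores marked at baseline.
 - 12.5.1.6: biopsy *and* tissue availability, stated as mandatory.

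 Most sections accept existing tissue. Only 12.5.1.6 reads as a flat requirement.

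5. **Same injury, two time points.**

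| | Fresh baseline biopsy, pre-dose | On-treatment biopsy |
|---|---|---|
| Inside the 6.1 window | No | Yes |
| Fits 8.1.1 as worded | No, patient not yet dosed | Yes |
| SAE sent to sponsor under 8.2 | No provision | Yes, whatever the relationship |
| Procedure-related category in 8.1.5 | None | None |
| Death within 30 days, not from progression | Clinical Director (7.3) | Clinical Director (7.3) |
| IRB policies 801/802 (7.2.1) | Possible; policy text not supplied | Possible; policy text not supplied |

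6. **Size.** The expected number of missed events is the number of fresh baseline biopsies times the serious complication rate. The documents give neither. Purely as an illustration, assume 38 to 75 biopsies (half to all of the 75-patient ceiling) and a rate of 0.5% to 3%. The expected count runs from 38 × 0.005 = 0.2 to 75 × 0.03 = 2.3. The chance of at least one runs from 1 − 0.995^38 = 0.17 to 1 − 0.97^75 = 0.90. All four inputs are assumptions, and a span from 17% to 90% shows only that the number is unknown.

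7. **The 8.3 pointer.** Section 8.1.6 lists the events of special interest and contains no report elements. Onset, severity, relationship, resolution and outcome are in 8.2.

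**The case against.** The best case for the current text is that it is coherent. Sections 6.1, 8.1.1 and 8.2 all describe a drug-focused window, and the safety objective concerns bintrafusp alfa, not biopsy. Serious harm from the same kind of procedure does reach the sponsor when it follows the on-treatment biopsy. A pre-dose biopsy may belong to 01-C-0129. Much of this stands, and it rules out several stronger readings that a reader might infer:

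- *That every patient must have a fresh baseline biopsy.* Most sections accept archival or existing tissue. The wording conflicts, and that is all that can be said.
- *That a complication would never be recorded anywhere.* Deaths within 30 days of a research intervention go to the Clinical Director under 7.3 unless due to progression. IRB policies apply under 7.2.1 with no first-dose start stated. Concomitant treatment is logged from consent. The gap is in this protocol's AE/SAE dataset and its sponsor reports.
- *That such an event already meets the SAE definition, so the protocol contradicts itself.* Section 8.1.2 does say that "a procedure required by the protocol, without a serious deterioration in health, is not considered a serious adverse event", but this qualifies the hospitalization criterion only. The section applies to adverse events, which 8.1.1 ties to a dosed subject.
- *That 17% to 90% is a risk estimate.* It is correct arithmetic on assumed inputs. The upper end needs every patient to have a fresh biopsy, and 12.5.1.3 describes significant complications as rare.

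What the objection does not remove is the gap itself. No section assigns the baseline research cores to 01-C-0129 or says that events under that protocol reach this study's sponsor. The IRB and Clinical Director routes do not place a non-fatal serious complication in this trial's safety data.

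**Conclusion.** The point holds in a limited form. When a fresh research biopsy is taken before the first dose, a non-fatal serious complication is not captured in this protocol's AE/SAE record and is not reported to its sponsor, and the protocol does not say who is responsible for it. This rests on the text of 6.1, 8.1.1, 8.1.5 and 8.2 and on the absence of any extending sentence. It does not depend on what 01-C-0129 or Policy 801 contain, because neither is said to feed this trial's record. The number of affected patients cannot be derived from the documents. Response rate, PFS, OS and the two-stage rules are unaffected. The change is worth making because it is cheap and the present rule loses events from a research procedure. The wrong pointer in 8.3 is a real but minor error, independent of the biopsy question.

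**What to change.** - In 6.1 and 8.2, record and report to the sponsor SAEs related to procedures required by this protocol, from the first such procedure after consent. List them separately from treatment-emergent events.
- Align 8.1.1 with that window, and add a category for events related to a study procedure in 8.1.5.
- State whether this protocol or 01-C-0129 covers the baseline biopsy. Reconcile the tissue wording in 2.1.1.8, 2.2.2, 5.1.7.1, 5.1.7.2, 12.5.1.6 and Appendix A note 1, and check it against the fresh cores marked in 5.2.
- In 8.3, point to Section 8.2 instead of Section 8.1.6.

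The cost is a few sentences and a few extra SAE forms, with no new visits or procedures. The reported count of procedure-related events may rise slightly, and the separate listing keeps those events out of the drug's safety profile.
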